1.0 Project Summary/Abstract

- *Orients the reviewer to the project.*
- *Provide a summary of the proposed activity that should be informative to other persons working in the same or related fields and insofar as possible understandable to a scientifically or technically literate lay reader.*
- *Schemas are welcomed and often provide a nice visual reference for the project.*

The goal of the proposed research is to achieve a major advance in promoting effective and efficient delivery of pediatric occupational therapy services towards improving participation-level outcomes for young children with developmental disabilities and delays. This research will examine the usability and feasibility of PEM-Plus, an innovative web-based (mobile friendly) care-planning guide, when used in conjunction with newly validated YC-PEM proxy questionnaire. PEM-Plus enables parents to design activity-specific solutions to their young child's participation-related problems in their own space and on their own schedule, as well as electronically share their solutions with providers and/or parents for improved care planning.

2.0 Background/Scientific Rationale

- *Describe the research problem and provide rationale for the research.*

The goal of the proposed research is to achieve a major advance in promoting effective and efficient delivery of pediatric occupational therapy services for young children with developmental disabilities. To evaluate PEM-Plus usability (Aim 1), ten parents will be recruited to perform tasks related to navigating the PEM-Plus interface. Data on completion rate and time, and user satisfaction, will be analyzed to guide PEM-Plus improvements. Then, in Aim 2, we will examine the feasibility and scientific basis for using the revised PEM-Plus to improve goal setting, care plan development, and parental self-efficacy. Study results will yield a final version of PEM-Plus that is ready for larger-scale testing in a pediatric efficacy trial. This project is aligned with the newly released AOTF research priority of improving care coordination towards improved participation in meaningful activities.

- *Briefly summarize prior experience and/or history relevant to the research.*

Members of our research team pioneered some of the first participation and environment measures that are commonly used in pediatric research and practice (Sections 1.3 and 1.4). The PEM approach represents a significant departure from prior efforts to measure children's participation because we explicitly combined the assessment of children's participation and environment within the same instrument. Development of a web-based application to help parents participate in planning their child's care is a highly innovative and logical next step for our research team. To our knowledge, no other group has developed a web-based application to empower and assist parents in developing their own solutions to promote their child's participation. We expect that PEM+ can advance the quality and efficiency of care planning in pediatric occupational therapy to achieve participation-level outcomes. Our multi-site, transnational research team has established an 8-year track record of continuous extramural funding. We developed and tested the PEM-CY and YC-PEM for research purposes and built a Knowledge Hub to facilitate knowledge uptake and resource exchange about children's participation and environment among key stakeholders (researchers, parents, and providers). We believe that PEM+ will significantly improve the uptake of the PEM approach in practice.

- For research involving the testing of drugs, biologics, or devices:
 - *Identify any investigational agents, drugs, devices, or biologics that will be administered or implanted into subjects.*
 - *Summarize relevant preclinical data*
 - *Summarize relevant clinical data to date*

- *Provide a rationale for the dosing or use of the device, risks to subjects, and potential benefits to subjects*
- *Discuss briefly any literature important to the study and include references in Section 14.*

3.0 Objectives/Aims

- *This section helps to clarify the questions the researcher expects to answer*
 - *Identify hypotheses being tested/primary endpoints/primary purpose of the protocol*

Aim 1 Objective: Examine the usability (technical effectiveness, efficiency, and user satisfaction) of the PEM+ interface by parents of young children with developmental disabilities and delays (Months 1-5).

Aim 2 Objective: Examine PEM+ feasibility and preliminary effects for goal setting and care planning (Months 6-12).

Hypothesis: Based on our prior intervention research to promote participation among children with physical disabilities, we expect that PEM+ will initially take up to 4 weeks with more intensive coaching support needed to generate viable activity-specific goals and action plans, and less time in subsequent iterations. There will be no significant age group differences in PEM+ feasibility.

- *Describe secondary endpoints (if applicable)*
- *Substudy endpoints (if applicable)*
- *Study duration*
- **Per funder guidelines, this project will be completed between 7/1/2016-6/30/2017.**

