4.0 Eligibility

- *Identify the subject population being evaluated by the protocol.*
- *Indicate the source of subjects.*
- *Identify who will assess and determine subject eligibility.*

Participants will be issued automated emails with study flyers to self-enroll in both aims of the project. Hence, all recruitment comes from UIC ([name]). Participants will self-enroll in the study and complete screening questions online to confirm eligibility. This confirmation of study eligibility will take place prior to online informed consent. We have successfully piloted this process in an NIH-funded pilot proposal, resulting in

enrollment of 39 study subjects in a 2-month period (IRB approval obtained in Colorado, at PI's prior institution, and is active from 2015-2016).

- *Indicate how and where eligibility will be documented.*

Participant confirms his/her eligibility based on a set of screening questions (e.g., what is your primary language, What is your child's date of birth, for how long has your child been receiving services). The portal and platform will no longer be hosted by Northwestern University. All data collected, including documenting participants who confirm their eligibility to enroll, via the web-based application that is being hosted via an Amazon cloud account will be pushed and stored in REDCap at UIC via API.

- *Attach an eligibility checklist to the protocol.*

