4.1 Inclusion Criteria

- 1) The inclusion criteria will no longer include the age group 4-5 year olds. It will include parent of a child with a developmental disability between 0-3 years old; 2) reads, writes, and speaks English; 3) owns a Mac or PC and has broadband internet access; and 4) resides in the U.S.

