For participants coming from Blue Bird Day School, those who sign a consent will fill out electronic forms for the YC-PEM and demographic information. Upon receipt, research staff will create a user account and manually enter consent, demographic, and YC-PEM data for the participant into the REDCap platform. Participants will be emailed a weblink to access their YC-PEM summary report when ready along with a link to begin the PEM+ usability test.

The PEM+ usability test will take 60 minutes and involve having participants complete a series of 8 tasks that correspond to key functions of PEM+ (e.g., you decide to go to sleep and wish to exit the platform after completing Step 1. Save your progress and log off). Following task completion, participants will complete the Single Ease Question (SEQ) after every individual task, while Usefulness, Satisfaction, and Ease of Use (USE) will be administered at the end of PEM+ to all participants. Each participant will receive a \$20.00 mailed payment.

For each of the 8 tasks, we will assess for Ease of Use, Ease of Learning, and Satisfaction at the end of PEM+, using the USE that estimates user satisfaction based on response to items on ease of use, ease of learning, and satisfaction (22 questions, each using a 7 point scale from [1] strongly disagree to [7] strongly agree). We will assess for overall ease using the SEQ after every individual task (1 question, using a 7 point scale from [1] very difficult to [7] very easy).

Aim 2 data source: There are 4 elements being assessed in this aim. For Process, data are derived via web analytics to ascertain recruitment and retention rates according to child's age. For Resources, data are also derived via web analytics for information about PEM-Plus completion time per iteration. For Management, web analytics are used to examine frequency and duration of tiered coaching (tier 1: videos, tier 2: email/text, tier 3: phone /Skype chat) and online progress notes entered into the platform by coaches are obtained to estimate type of support. For Scientific basis (preliminary effects), data sources are as follows: 1) web analytic data are used to estimate number of goals set and strategies developed in 4 weeks, and 2) modified CanChild Survey completion at 4 weeks is used to estimate perceived effectiveness of PEM-Plus for goal setting and strategy development

Aim 2 Sampling and Data Collection:

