We will build on Aim 1 recruitment strategies to recruit 24 parents of children with developmental disabilities ages 0-3 years for PEM+ feasibility testing. The sample size estimate is similar to prior studies on participation outcomes (Verhoef, Miedema, Van Meeteren, Stam, and Roebroeck, 2013) and feasibility considerations. We will target recruitment of children in 1 age group (infants and toddlers between 0-3 years) to examine the feasibility of PEM+. Inclusion criteria: Same as Aim 1.

Automated email with study flyer will be sent to families on listserves. Parents who meet eligibility criteria will be directed via web link to create a user account to enter the YC-PEM study platform that is being hosted on REDCap at UIC. Participants will provide online consent and then proceed in completing a demographic questionnaire and YC-PEM online to receive a summary report, followed by phone consultation to interpret their report. Participants will then click a web link on the YC-PEM report to be directed to a revised PEM+ platform hosted via combination of Amazon cloud and REDCap at UIC. Participants will proceed through PEM+ to apply information from the report to generate participation goals for their child and potential intervention strategies. Parents will be given 4 weeks to develop as many goals and intervention strategies as possible, and they may opt for help using one or more of the following options for support: 1) text-based examples of priorities, goals, and strategies that are accessed by the parent in the PEM+ platform, 2) email coaching support (parent clicks on a link in the platform to email trained UIC staff with questions), and/or 3) phone or video conferencing (Skype) consult that participant can request in the platform, to be provided by master coach ([name]). No more than 6 participants will begin PEM+ each week to ensure feasibility, resulting in a total of 8 weeks for data collection (6 participants/week x 4 weeks/participant). Weekly text-message and email reminders will be issued to all participants to promote retention and completion rates. Final phone consultation and CanChild survey completion will take place at 4 weeks. Each participant will be paid \$80.00 at 4 weeks (\$40.00 prorated payment for completion of no more than 2 weeks).

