Participation and Environment Measure-Plus (PEM-Plus) Care Planning Intervention

NCT Number: 03820011

Date: June 17, 2017

Aim 1 Statistical Plan:

Demographic and usability data were exported via REDCap, and an administrative dashboard for analyses. Demographic characteristics and YC-PEM summary scores were reported for each user. To address the main study question, usability estimates were derived for the total study sample, according to technical effectiveness (PEM+ min-max and mean percent completion rate, mean completion time, and mean task difficulty rating), and USE summary scores (mean and range) for ease of use, ease of learning, and user satisfaction.

Aim 2 Statistical Plan:

All analyses were completed on the total sample and age subgroups (0-3 years, 4-5 years) using SPSS 24.0. The primary study aim was to assess for PEM+ feasibility and acceptability. To assess for PEM+ feasibility, retention rate, median completion time of first iteration, median completion time of subsequent interactions, and use of tiered support were reported. To assess for PEM+ acceptability, total scores were reported as means with standard deviations. Additionally, open-ended responses were independently coded by four research team members to sort caregiver feedback regarding the acceptability of PEM+ into categories.

As a secondary aim, preliminary effects mean self-efficacy item scores were calculated and Pearson correlations were used to ascertain associations between proportion of care plans created, relative to areas of desired change, with caregiver self-efficacy scores.

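### The Aim 2 age hypothesis is met by a non-significant result, and 24 participants cannot support a conclusion of no age difference

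*Protocol*

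**What the plan says.** Protocol section 3.0 states, under the Aim 2 hypothesis: "There will be no significant age group differences in PEM+ feasibility". No margin of acceptable difference accompanies it.

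Section 6.0 plans to "recruit 24 parents of children with developmental disabilities ages 0-3 years for PEM+ feasibility testing". The justification is that "The sample size estimate is similar to prior studies on participation outcomes", together with feasibility. No power or precision calculation is given. Protocol sections 9.0 and 12.0 contain only template prompts, so no test or significance level is stated there.

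On age, section 4.1 says "The inclusion criteria will no longer include the age group 4-5 year olds", section 4.2 excludes parents of children over 3, and section 6.0 says "We will target recruitment of children in 1 age group (infants and toddlers between 0-3 years) to examine the feasibility of PEM"+. Age breakdowns nevertheless remain. The Aim 2 data-source text in section 6.0 uses "web analytics to ascertain recruitment and retention rates according to" the child's age, and the SAP's Aim 2 plan says "All analyses were completed on the total sample and age subgroups (0-3 years, 4-5 years) using SPSS 24.0".

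The SAP reports the feasibility measures descriptively: retention, median completion times and use of tiered support. The only inferential method it names is Pearson correlation, for the self-efficacy scores.

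**The concern.** The hypothesis predicts the null result. It is satisfied whenever a comparison fails to reach significance, and a small study fails to reach significance easily whether or not the groups differ. With no margin, nothing separates finding the age groups similar from being unable to tell.

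Section 2.0 says the results should yield a version of PEM+ ready for a larger efficacy trial. If a no-age-difference statement went forward from this study, that trial could leave age out of its design or its coaching plans, on data that are compatible with large differences.

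**Working it through.** **The plan's own figure.** The 24 cannot be reproduced. No effect size, significance level, power, margin or dropout allowance is given.

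**Inputs.** From the documents: 24 participants, and retention as a feasibility outcome to be looked at by age. Assumed, because the documents are silent: two age groups, split 12:12 (also 16:8, 18:6 and 8:16); two-sided 5%; and a true 30-point retention gap, with 90% versus 60% as the main case and a range from 100/70 to 65/35.

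**Step 1: normal approximation at 12:12, 90% versus 60%.** With mean rate 0.75:

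z = [0.30 × √12 − 1.96 × √(2 × 0.75 × 0.25)] / √(0.9 × 0.1 + 0.6 × 0.4) = (1.039 − 1.200) / 0.574 = −0.28

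Power is therefore about 39%, so the result is non-significant about 61% of the time.

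**Step 2: exact enumeration.** Sum the binomial probabilities of every pair of retained counts for which the test gives p > 0.05. Percentage of studies that are non-significant (the first-named group has the higher retention):

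| Split | True retention | Normal approx. | Chi-square | Fisher |
|---|---|---|---|---|
| 12:12 | 90 v 60 | 61.0 | 61.3 | 76.7 |
| 12:12 | 65 v 35 | 69.6 | 64.2 | 78.9 |
| 12:12 | 100 v 70 | 45.7 | 49.3 | 72.4 |
| 16:8 | 90 v 60 | 58.3 | 56.1 | 68.2 |
| 16:8 | 95 v 65 | 50.7 | 47.9 | 62.3 |
| 16:8 | 100 v 70 | 39.0 | 25.5 | 55.2 |
| 18:6 | 90 v 60 | 59.5 | 57.5 | 71.1 |
| 18:6 | 100 v 70 | 38.1 | 42.0 | 74.4 |
| 8:16 | 90 v 60 | 70.8 | 65.4 | 85.5 |
| 8:16 | 100 v 70 | 63.5 | 66.0 | 92.6 |

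Over all 28 combinations of split and rates tried, Fisher runs from 55% to 93%. Every value below 50% is in this table. All come from chi-square or the normal approximation, with retention of 95% or 100% in the better group.

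**Step 3: one outcome that can be checked by hand.** Suppose 11/12 and 7/12 are retained, an observed gap of 33 points. Fisher's two-sided p = 2 × (12 × 792 + 1 × 924) / 134,596 = 0.155. The chi-square statistic on the z scale is 0.333 / √(0.75 × 0.25 × 2/12) = 1.89, below 1.96. Both are non-significant, so the hypothesis would be met.

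**Step 4: precision when the groups look identical.** Let both groups retain 10/12 (0.833). The Wilson 95% limits for each are 0.552 and 0.953. Newcombe's limits for the difference are ±√[(0.833 − 0.552)² + (0.953 − 0.833)²] = ±0.306, or about -31 to +31 points.

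**Step 5: scale of a study that could address the question.** Detecting 90% versus 60% with 80% power needs (1.96 × 0.612 + 0.842 × 0.574)² / 0.30² = 31.5, so 32 per group (64 in all). Showing equivalence within an illustrative 20 points, if both groups truly retain 80%, needs 2 × 0.8 × 0.2 × (1.645 + 1.282)² / 0.20² = 68.5, so 69 per group (138 in all). If both retain 90%, it is 39 per group (78 in all).

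**The case against.** The strongest reply is that no such test is planned. The SAP reports feasibility measures descriptively, names no between-group test and sets no decision rule, so the test, the level, the split and the rates above are all assumptions. This stands, and the figures should be read as a range. It does not rescue the sentence: a hypothesis about significance calls for a test, and leaving the test, margin and interpretation unstated leaves the problem open.

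A second reply is that the comparison has no groups. All 24 participants are to be 0-3 years old, so the sentence looks like a remnant of a two-band design. The contradiction is real and arguably more basic. Repairing the bands alone would still leave the inference faulty, and both documents still break results down by age.

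Three stronger readings are tempting but not supported:

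- A reader might infer that the investigators will claim equivalence. Neither document says how a non-significant result will be interpreted.
- A reader might infer that a non-significant result is almost certain. The figures show it is usual under most assumptions, and less likely than not in a few.
- A reader might extend the calculation to completion time with a two-sample t-test. The SAP summarises completion time by medians and gives no variability, so no such figure is used here.

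**Conclusion.** The point holds in a limited form. The hypothesis as worded is met by non-significance, and 24 participants cannot support a no-difference conclusion. At 12:12 and a two-sided 5% level, a true 30-point retention gap (90% versus 60%) would be missed in roughly three to four of every five studies, depending on the test. The most robust figure is the interval, which needs no assumption about the true rates or the significance test: perfect observed agreement at 10/12 would still not exclude a 30-point difference in either direction. It does rest on an even split and on that retention level.

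The descriptive feasibility results for the whole sample are not affected. What is affected is any statement about age.

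**What to change.** Delete the age sentence from protocol section 3.0, or replace it with an estimation aim such as: We will describe retention and first-iteration completion time by the child's age, with 95% confidence intervals. This is exploratory, and no conclusion of similarity will be drawn from a non-significant result. Put a matching sentence in the SAP's Aim 2 plan.

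The child's date of birth is already among the screening questions in section 4.0, so no new data are needed. Age in months could be used within the single 0-3 group without inventing new bands, though that is a choice and not a requirement.

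In the same edit, reconcile section 3.0 and the SAP's 0-3 and 4-5 subgroups with the 0-3-only eligibility in sections 4.1, 4.2 and 6.0.

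If a similarity claim is wanted, state a margin in advance and require the confidence interval to lie inside it. For a margin such as 20 points, that calls for a study several times larger than 24.

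The cost is about one sentence in each document plus the subgroup reconciliation, and giving up a no-age-difference claim that the study could not have supported.

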4.0 Eligibility

- *Identify the subject population being evaluated by the protocol.*
- *Indicate the source of subjects.*
- *Identify who will assess and determine subject eligibility.*

Participants will be issued automated emails with study flyers to self-enroll in both aims of the project. Hence, all recruitment comes from UIC ([name]). Participants will self-enroll in the study and complete screening questions online to confirm eligibility. This confirmation of study eligibility will take place prior to online informed consent. We have successfully piloted this process in an NIH-funded pilot proposal, resulting in

enrollment of 39 study subjects in a 2-month period (IRB approval obtained in Colorado, at PI's prior institution, and is active from 2015-2016).

- *Indicate how and where eligibility will be documented.*

Participant confirms his/her eligibility based on a set of screening questions (e.g., what is your primary language, What is your child's date of birth, for how long has your child been receiving services). The portal and platform will no longer be hosted by Northwestern University. All data collected, including documenting participants who confirm their eligibility to enroll, via the web-based application that is being hosted via an Amazon cloud account will be pushed and stored in REDCap at UIC via API.

- *Attach an eligibility checklist to the protocol.*

4.1 Inclusion Criteria

- 1) The inclusion criteria will no longer include the age group 4-5 year olds. It will include parent of a child with a developmental disability between 0-3 years old; 2) reads, writes, and speaks English; 3) owns a Mac or PC and has broadband internet access; and 4) resides in the U.S.

4.2 Exclusion Criteria

- 1) Exclusion criteria will no longer include parent of a child more than 5 years old. It will include parent of a child more than 3 years old; 2) does not read, write, and speak in English, 3) does not have broadband internet access, or 4) does not reside in U.S.

4.3 Excluded or Vulnerable Populations

For Aim 2, respondents are not eligible if they do not speak English (because the questionnaires are only available in English), are less than 18 years old.

5.0 Subject Enrollment

- *Describe screening and enrollment.*
- *Describe from where subjects will be recruited and any advertising or recruitment materials that will be used.*
- Participants self-enroll online via web link on flyer and provide online consent via the first part of the platform being hosted in REDCap at UIC. The first part of the platform involves consent, demographic, and YC-PEM completion. Hence, UIC ([name])

- *Describe what happens with screen failures and any data obtained from screen failures.*
- *Describe the methods to minimize coercion and undue influence on the subjects.*
- Automated emails and study flyers will be sent to families in 2 listserves. These families have enrolled in prior research in Colorado and have consented to future contact. Eligible and interested caregivers will self-enroll in the study and self-administer the questionnaires and care planning guide. Caregivers can enroll on their personal computer, using information including weblink to study site that is located on the study flyer. Hence, all data collection can occur outside of research involvement and/or service provision to minimize undue coercion on study enrollment. Once enrolled, no providers and/or family members will know which caregivers have enrolled unless the caregiver chooses to share his/her summary report with him/her.
- *Describe the procedures to separate clinical responsibilities and influence from research responsibilities and influence.*

